9. COMPLIANCE WITH AFZAAISH SUPPLEMENT AND AZITHROMYCIN

Although, every woman enrolled and randomized, will be included in intention to treat analysis, however for the purpose of trial administration and assurance of maximum compliance, the following criteria will be followed to define compliance:

- a) Team will be tasked to ensure at least 75% compliance in each month with the consumption of a supplement which will be given to LW enrolled in Arm B and C

Compliance (for 6 months)	100% Compliance in each month	75% Compliance in each month	Low compliance and concern for counseling
Afzaaish related- 2 sachets of Afzaaish to be consumed in 24 hours	If 60-65 sachets consumed in 30 days	If 45-49 sachets consumed in 30 days	LW who has consumed <45 sachets for 2 consecutive months (based on each month's compliance)

- b) Team will ensure that dose of Azithromycin was administered on 42 days (window period of 7 days).
- c) Exclusive Breastfeeding: Team will be tasked to achieve at least 75% compliance each month in all arms

Compliance (for 6 months)	100% Compliance in each month	75% Compliance in each month	Low compliance and concern for counseling
Only breastfeeding from LW enrolled in the trial, with no other things to drink or eat given to child	Only breastfeeding from LW enrolled in the trial, with no other things to drink or eat given to child, confirmed on each visit	If based on 24 hours recall, each month cumulative % of breast milk attempt is within 75% of the acceptable limit	If based on 24 hours recall, each month cumulative % of breast milk attempt calculated is <75% ,it falls under the non per protocol limit

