Analysis approach

Statistical analysis will be performed by Stata, version 15. The baseline characteristics will be assessed by arm. The primary analysis will be an intention-to-treat (ITT) analysis. We will compare the mean length velocity (cm/ month) (primary outcome), weight velocity (gm/kg/day), LAZ, WLZ, and WAZ between the two intervention arms and the control arm using ANOVA, with the model adjusted for the birth weight and age of the infants at enrollment. If an outcome is missing for the intention-to-treat infants, the means from that group will be imputed.

Safety outcomes

i. Maternal serious adverse events

The occurrence of maternal SAEs will be expressed as the proportion of women with at least one SAE during the follow-up period (from enrolment to 179th day). The proportion will be calculated by dividing the number of women with at least one recorded SAE by the total number of enrolled participants. Results will be shown both as proportions of participants with any SAE as well as tabulated by the SAE category (death, hospitalization, other). If any participant has experienced more than one type of SAE, the participant will be recorded in each category.

ii. Infant serious adverse events

The occurrence of infant SAEs will be expressed as the proportion of babies with at least one SAE during the follow-up period (from enrolment to 179th day). The proportion will be

calculated by dividing the number of babies with at least one recorded SAE by the total number of recorded newborns. Results will be shown both as proportions of participants with any SAE as well as tabulated by the SAE category (death, hospitalization, other). If any participant has experienced more than one type of SAE, the participant will be recorded in each category.

Interim analysis

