11. SAMPLE SIZE CALCULATIONS & POWER ANALYSIS

The sample size is calculated and powered to look at multiple comparisons, between arms A and B, A and C plus B and C with a hypothesized higher increase with addition of Azithromycin to infant with Afzaaish in LW. Also, adjustment for multiple comparison is needed. Thus, calculations for the sample size is estimated and are per arm sample size is provided below based on the primary outcome of length velocity in LW trial with 1-sided testing, alphas to account for multiple comparison (the lower alpha), and drop out of 14% is assumed in the trial.

Assumptions for Sample Size Calculations

Variable	Difference	Std Dev	Alpha	Drop out portion	n/arm	n/arm adj dropout	Actual Power
Length Velocity	0.12	0.5	0.025	0.14	274	319	0.801

Based on assumptions, a sample size of 319 children per arm is calculated, assuming 14% drop out rate (i.e. 10% margin for loss to follow up, and 4% infants deaths).

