The null hypothesis for this trial is that the mean difference in length velocity between an infant of a lactating woman receiving standard breastfeeding counseling with BEP alone (Intervention arm 1) for 6 months or in combination with a single prophylactic dose of azithromycin at 42 days of age (Intervention arm 2) and an infant of a lactating woman receiving standard breastfeeding counseling alone (control arm) is equal or less than 0.12 cm/month (primary outcome). Due to the absence of evidence of such interventions on length velocity, we based this hypothesis on our local experience and field data from our field sites. The alternate hypothesis for this trial is that an infant of a lactating woman receiving BEP alone for 6 months or in combination with a single prophylactic dose of azithromycin at 42 days of age has a mean length velocity is greater than 0.12 cm/month that of an infant of a lactating woman not receiving an intervention at 6 months. The sample size takes multiple comparisons into account and is based on the primary outcome of length velocity with an effect size of difference of 0.12 cm per month between the arms (i.e., 0.72 cm difference at 6 months), a 1-sided test, power of 80% and an alpha of 0.025 to account for multiple comparisons (the lower alpha – Bonferroni correction was used). A drop-out rate of 14% (i.e., 10% loss to follow up and infant mortality rate of 4%) is assumed in the study, so the minimum total sample size required is 957 (319 lactating women in each arm).

7. Eligibility criteria

Inclusion Criteria

- a) Lactating women with a mid-upper-arm-circumference (MUAC) of < 23.0 cm
- b) Infants with a live birth outcome, captured within 168 hours (0-6 days)
- c) Individuals with the intention to stay in the catchment area for entire duration of trial after enrollment
- d) Individuals with the intention to exclusively breastfeed child for at least 6 months of age
- e) Individuals who have provided voluntary written informed consent

Exclusion Criteria

- a) Newborns with a birth weight of less than 1500 grams
- b) Newborns with a known congenital anomaly or other severe illness based on the study physician's assessment before enrollment.
- c) Lactating women with known allergies to peanut, lentils, chickpea or dairy products
- d) Individuals who were previously enrolled in the trial

8. Blinding

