The primary analysis will be by intention-to-treat (ITT) perform for those who had anthropometry at 6 months. All analyses will be done using Stata software version 16. The WHO 2009 Child Growth Standards will be used for age-sex standardization of child length, weight, head circumferences, MUAC and weight-for-height. Descriptive analysis of each arm will be conducted, and percentages or continuous data with SD will be reported.

The baseline characteristics will be assessed by arm. Outcomes of mean length velocity, growth velocity, weight gain, z scores and change in z score from 0-6 month will be compared using one way analysis of variance (ANOVA). Tukey's test will be used for multiple comparisons. As determined *a priori* the analysis will be adjusted for the birth weight and length of infant, maternal MUAC at enrollment, maternal age, gravida, maternal body mass index and gender of child using general linear model (GLM). Mixed model analysis will be used to compare change in outcome per month in the intervention arm compared to the control arm. Using repeated measures ANOVA, the analysis will report beta coefficients and 95% CI. The coefficients represents the rate of change in outcome per month. For covariate adjustment, an unadjusted and stepwise adjusted model will be run. Trajectories will be plotted for mean length and weight by age for each arm, and monthly z scores were also be plotted.

13. Potential sub-group analysis

The following variables will be considered for sub-group analysis for primary and secondary outcomes:

1. Birth weight i.e. <2500 gm and => 2500 gm
2. Maternal MUAC at enrolment i.e. < 21.0 cm and =>21.0 cm
3. Maternal age i.e. <30 years and => 30 years
4. Gravidity i.e. <3 and =>3
5. Maternal BMI i.e. <18.5 kg/m² and =>18.5 kg/m²
6. Gender of child

14. Missing Data

We will treat missing data as it is, no imputation will be applied. We discussed that due to growth flattering during this age, imputation maybe unreliable.

15. Interim analysis

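### The protocol fills a missing outcome with the group mean, while the SAP imputes nothing and calls 6-month completers ITT; the protocol rule would run the one-sided 0.025 test at about 0.046

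*Protocol*

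**What the plan says.** Protocol section 10 (Analysis approach) makes the ITT analysis primary. It compares arms by ANOVA adjusted for birth weight and age at enrolment, and then states: "If an outcome is missing for the intention-to-treat infants, the means from that group will be imputed". Protocol section 9 sets the population: "every woman enrolled and randomized, will be included in intention to treat analysis".

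SAP section 12 also uses the ITT label, for a different set: "The primary analysis will be by intention-to-treat (ITT) perform for those who had anthropometry at 6 months". SAP section 14 reads: "We will treat missing data as it is, no imputation will be applied". The reason it gives is that imputation may be unreliable for growth at this age. The same section 12 plans a longitudinal analysis: "Mixed model analysis will be used to compare change in outcome per month in the intervention arm compared to the control arm".

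Protocol section 11 sizes the trial "assuming 14% drop out rate (i.e. 10% margin for loss to follow up, and 4% infants deaths"). SAP section 6 gives the test used for sizing: "a 1-sided test, power of 80% and an alpha of 0.025 to account for multiple comparisons".

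**The concern.** Both rules apply to the primary outcome, and the SAP does not mention the protocol's rule or say that it replaces it.

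If the group is the randomised arm, filling in its mean leaves the unadjusted arm means exactly as they were, so no bias is corrected. What changes is the apparent precision. The added records sit on the arm mean, the within-arm variance shrinks, n rises, and the standard error comes out too small. Infants who died would receive the mean velocity of the measured infants if a death counts as a missing outcome. The drop-out allowance suggests that reading, since it includes deaths.

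The SAP rule has no false precision. Its difficulty is the population: it omits randomised infants without a 6-month measurement, so it does not match protocol section 9. Its adjusted estimate is unbiased if, given arm and the adjusted covariates, missing the visit is unrelated to length velocity.

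While both rules stand, the choice between them could be made after the data are seen.

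**Working it through.** **Inputs.** From protocol section 11: difference 0.12 cm/month, SD 0.5, alpha 0.025, drop-out 0.14, 274 evaluable and 319 randomised per arm, power 0.801. So 319 − 274 = 45 per arm are missing. Assumptions: arm-mean imputation, equal loss in each arm, data missing completely at random.

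**The plan's own figures.** A one-sided 0.025 two-sample test at 80% power needs 273 per arm by the normal approximation and 274 by the noncentral t (power 0.801). Then 274/0.86 = 318.6, rounded up to 319. The stated figures reproduce.

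**True standard error of an arm difference.** 0.5 × √(2/274) = 0.0427 cm/month.

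**Reported standard error under the protocol rule.** The within-arm sum of squares is unchanged, but the variance divisor goes from 273 to 318 and n from 274 to 319:

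- ratio = √[(273/318) × (274/319)] = 0.8587
- reported SE = 0.0427 × 0.8587 = 0.0367 cm/month

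**Error rate and coverage.**

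- one-sided error = 1 − Φ(1.96 × 0.8587) = 1 − Φ(1.683) = 0.0462, against 0.025
- coverage of a nominal 95% interval = 1 − 2 × 0.0462 = 0.908

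**Sensitivity to the share imputed.**

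| Missing | Observed + imputed per arm | SE ratio | One-sided error |
|---|---|---|---|
| 5% | 303 + 16 | 0.9498 | 0.031 |
| 10% | 287 + 32 | 0.8995 | 0.039 |
| 14% | 274 + 45 | 0.8587 | 0.046 |
| 20% | 255 + 64 | 0.7991 | 0.059 |

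**Other tests.** The analysis sections name ANOVA, and the SAP adds Tukey. Neither section states a level, so 5% is assumed here. The three-arm F test runs at P[F(2, 819) > F_crit(2, 954) × 0.8587²] = 0.110. By simulation, the Tukey familywise rate is about 0.108.

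**Covariate adjustment.** Imputed values carry no relation to the covariates, so the adjusted model was simulated: 20,000 null three-arm trials per setting, two covariates, assumed covariate-outcome correlation 0, 0.3 and 0.5.

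| Rule | Pairwise one-sided error | F test at 5% |
|---|---|---|
| Arm-mean imputation | 0.0460, 0.0464, 0.0470 | 0.110, 0.105, 0.112 |
| No imputation | 0.0260, 0.0250, 0.0245 | 0.0505, 0.0475, 0.0498 |

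**Can the choice change the conclusion?** Against a zero difference, which is the reading under which the stated power reproduces, the smallest significant observed difference is 1.96 × 0.0427 = 0.084 cm/month under the SAP rule and 1.96 × 0.0367 = 0.072 under the protocol rule. A result between the two is significant under one document only.

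**Deaths.** 0.04 × 319 = 12.8, about 13 infants per arm; 0.04 × 957 = 38.3, about 38 in total.

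**The case against.** The strongest reply is that the SAP is the dedicated analysis document and reads as the later one: it names Stata 16 where the protocol names 15, and it considers imputation and declines it with a reason. On that view the protocol sentence is a leftover and the 0.046 will never arise. This is plausible, but the available text of neither document says so. The title pages could not be consulted, so a precedence statement there cannot be excluded. Even if the SAP governs, the mismatch with protocol section 9 remains.

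Four further points have some force.

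- The one-sided 0.025 test comes from the sample-size sections, not the analysis sections. That is right, but the inflation is also about twofold for the F and Tukey tests.
- The protocol's definition of length velocity uses every four-weekly measurement, so an infant who misses only the last visit might still have a velocity. Fewer values would then be imputed; at 5% the error is 0.031. The SAP's two-point definition does not allow this reading.
- Analysing available outcomes by randomised arm is often called ITT, and the SAP states its set openly. The label still contradicts the protocol's own description.
- SAP section 8 keeps the final analyst blinded until results have been shared. This reduces the risk of a choice driven by results, but does not remove it.

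**Conclusion.** The concern holds and should be fixed before analysis. The two missing-data rules contradict each other, the SAP's ITT set is a completers' set, and no precedence is stated in the available text.

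The protocol rule is wrong as written, because it reports a standard error about 14% too small (ratio 0.859) at the planned loss. The error rate of 0.046 in place of 0.025 applies only if that rule is used. It assumes 14% missing in each arm, the arm as the group, and data missing completely at random; any selection bias would be additional. Under that same missingness assumption, the SAP rule keeps the nominal error rate and the planned power.

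**What to change.** 1. Delete the imputation sentence from protocol section 10 and state the no-imputation rule in both documents.
2. Label the 6-month analysis complete-case, by randomised arm. Align the ITT wording in protocol sections 9 and 10 and SAP section 12 in the same edit.
3. Keep two-point length velocity as the primary endpoint.
4. Prespecify the planned mixed model of the monthly measurements as a sensitivity analysis under missing at random, using every infant with a baseline and at least one later measurement.
5. State how infants who died are handled in each analysis. The mixed model implicitly projects their lengths to 6 months, so silence is itself a choice.
6. Report missing 6-month outcomes and deaths by arm. SAP Table 3 already has space for the analysed N and infant deaths, so this adds little.

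The cost is wording in two documents and a modest amount of analysis on data already being collected. The reported standard error will be 0.0427 instead of 0.0367 cm/month, which is the correct value under the planning assumptions. No planned power is lost: with 274 per arm, Φ(0.12/0.0427 − 1.96) = 0.80, as the protocol states.

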8.2. Azithromycin related – Infant only

To establish safety profile for AZM prophylaxis dose, the infant will be monitored for the next 48 hours. After administration, data will be collected and any side-effects (observed or reported) will be noted by the research team. They will revisit the infants after 24 hours (i.e. after dose, two consecutive visits will be performed with a 24 hour gap). For this trial the data collected on adverse events and other related reports will be provided by Principal Investigator directly to the DSMB on a monthly basis (serious) in the form of report, while any fatal adverse events will be reported to DSMB and AKU/VPT IRB within 72 hours of event reported.

Adverse event reporting form will be filled against every event which is reported over the course of study period and in case of any death the routine verbal autopsy form will also be filled. Based on the information provided in the forms, decision will be made on whether to classify the event as serious or non-serious and also if it was related to trial intervention or not. Post-dose (43 and 44 day) visits will be performed to monitor and observe any suspected adverse event in the infants which are most likely to appear after AZM administration. If in any case, the dose is delayed, the 2 consecutive visits days will be changed accordingly.

Adverse and serious adverse event reporting and categorization

Based on the literature (30), following potential adverse event in infants related to AZM will be monitored:

- i. Gastrointestinal:
 - a. Vomiting: Persistent vomiting or projectile vomiting in an infant reported by mother, within 24 hours of dose administration (Observed or reported).
 - b. Poor feeding/suck: If an infant develops poor feeding/suck or is unable to feed within 24 hours of dose administration (Observed or reported).
 - c. Necrotizing Enterocolitis: Abdominal distention/tenderness, bowel movements, signs of infection such as apnea (stop breathing), and lethargy within 24 hours of dose administration in an infant (Observed or reported).
 - d. Diarrhea: Loose stool in an infant reported by mother, lead to severe dehydration, within 24 hours of dose administration (Observed or reported).
- ii. Respiratory:
 - a. Respiratory distress: Fast breathing (60 or more breathes per minutes) and/or severe chest in drawing and/or baby turn bluish, within 24 hours of dose administration (Observed or reported).

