Data Safety and Monitoring Board of the trial will request an independent statistician to run interim analysis when 50% of the enrollment will complete the 6 months follow-ups in the trial. The analysis will be coded and the findings will on difference in primary, secondary outcomes and Serious Adverse Events will be shared to DSMB in blinded coding. The DSMB will review results from the interim data analysis and will determine whether stopping boundaries have been crossed. Additional interim analyses may be completed and reviewed by the DSMB, per the advisement of the DSMB chair. The DSMB may, at its own discretion, ask the interim analysis to be done earlier or additional interim analyses to be completed on an ad hoc basis.

For any interim analysis, the data management team at the VPT will prepare a blinded, cleaned analysis database. The interim analysis will be conducted on a blinded basis, as follows: Project data team at VPT will prepare and verify interim analysis programs using randomly generated dummy treatment assignments that have no relationship to the true intervention assignments. An independent statistician will subsequently incorporate blinded treatment codes group 1, 2 and 3 for safety end points status. The data team will separately provide treatment codes to the chair of the DSMB in a sealed file. At a minimum, the results to be presented will include a summary of screening and enrollment status, descriptive statistics of baseline variables, summaries of protocol violations, serious adverse events, primary, and secondary growth outcome. Site-specific and overall results will be pooled over treatment groups. DSMB may request other analyses as it deems fit. The DSMB will decide whether or not they wish to open the treatment code envelopes to un-blind themselves.

i. Stopping guidelines / Stopping rules

Based on the trial safety monitoring and interim analysis, the following may be the key decision/s of DSMB pertaining to the trial:

- a) No action needed, trial continues as planned.
- b) Early stopping due, for example, to clear benefit or harm of an intervention/s, uselessness, or external evidence.

- c) Extending recruitment (based on actual control arm response rates being different to predicted rather than on emerging differences) or extending follow-up.
- d) Stopping an arm of the multi-arm trial.
- e) Sanctioning and/or proposing protocol changes

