While stopping rules will be utilized to help the DSMB to assess the justification of trial continuation, the DSMB will take into account the balance of risks and benefits as well as consistency with external evidence. Thus, the DSMB recommendation to continue or discontinue will not be based on any single issue or value in any of the analyses, but a comprehensive analysis taking into account multiple issues around the trial.

The DSMB may recommend termination or modification of the study if:

- i. In an interim analysis, there is strong evidence of a benefit (increases length velocity and/or secondary outcome) from the study intervention (O'Brien Fleming rule, $p < 0.005$).
- ii. In an interim analysis, there is strong evidence of harm (incidence of SAEs) from the study intervention. For harm assessment, no fixed statistical rules will be applied, but the DSMB will holistically consider point estimates and confidence intervals for SAE incidence differences, p-values from appropriate statistical tests and other relevant factors, when determining its recommendation about study continuation or discontinuation.

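### The Protocol says both that interim results are pooled over arms and that the DSMB sees them by coded arm; separately, non-fatal life-threatening events have no stated reporting route faster than monthly

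*Protocol*

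**What the plan says.** **Interim content.** Protocol section 10, Interim analysis, sets the minimum DSMB report. Besides enrolment status and baseline data it includes "summaries of protocol violations, serious adverse events, primary, and secondary growth outcome". The next sentence reads "Site-specific and overall results will be pooled over treatment groups". It makes no exception for safety or for the growth outcomes.

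The same subsection also says "the findings will on difference in primary, secondary outcomes and Serious Adverse Events will be shared to DSMB in blinded coding", and "An independent statistician will subsequently incorporate blinded treatment codes group 1, 2 and 3 for safety end points status". It adds "The data team will separately provide treatment codes to the chair of the DSMB in a sealed file". The DSMB may request further analyses, may call for earlier or additional interims, and may unblind itself.

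**Use of the content.** The stopping guidelines in the same section set no fixed boundary for harm. The DSMB is to "holistically consider point estimates and confidence intervals for SAE incidence differences", together with p-values. A benefit rule refers to length velocity and secondary outcomes, and stopping one arm is a listed decision. SAP section 15 repeats the coded-difference statement and the harm rule but contains no pooling sentence. SAP section 8 describes the interim analysis as blinded by arm.

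**Reporting between interims.** Protocol 8.1 (mothers, supplement) and 8.2 (infants, azithromycin) send serious events to the DSMB in a monthly report, "while any fatal adverse events will be reported to DSMB and AKU/VPT IRB within 72 hours of event reported". Both sections count a life-threatening situation as an SAE and rate each suspected event on a relatedness scale that runs up to definitely related.

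**The concern.** There are two separate points.

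(a) The statistician who prepares the interim tables cannot both pool the overall results over arms and show them by coded group. The choice matters because the harm judgement has no numerical boundary and so depends on what the DSMB is shown. A harm confined to one arm is diluted in a pooled table, and a pooled table yields no difference, interval or p-value. The benefit rule and any decision to stop one arm have the same need.

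(b) A non-fatal life-threatening event, even one rated definitely related to azithromycin or the supplement, has no stated route to the DSMB faster than the monthly report. Neither 8.1 nor 8.2 states that it goes to the IRB. Under 8.2, infants are visited on days 43 and 44 to look for reactions to a day-42 dose. An event found then could wait up to a month before the DSMB sees it.

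**Working it through.** **Point (a): the texts side by side**

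| Place | Instruction | Form of results |
|---|---|---|
| Protocol 10, Interim analysis, first paragraph | Differences in primary, secondary and SAE outcomes go to the DSMB | Coded arm |
| Same, second paragraph | Independent statistician adds codes 1, 2 and 3 for safety | Coded arm |
| Same, sentence after the minimum content | Site-specific and overall results | Pooled |
| Protocol 10, stopping guidelines | SAE incidence differences, intervals, p-values; benefit rule; stopping an arm | Needs arms |
| SAP 15 | Coded differences; same harm rule | Coded arm |

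One sentence is out of line with the other four. The Safety outcomes text in Protocol section 10 does not settle the matter: it divides SAEs by all enrolled participants or all recorded newborns without saying by arm.

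**What pooling would hide (illustration)**

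1. Interim size. Protocol section 11 gives 274 per arm and 14% dropout: 274/(1 − 0.14) = 318.6, or 319, as stated. The interim falls when 50% have completed follow-up: 319 × 0.5 = 159.5, about 160 per arm and 480 in all.
2. The documents give no expected SAE risk, so the counts are assumed. Compare two splits over three arms: 10/10/11 and 6/6/19.
3. Pooled: (10 + 10 + 11)/480 = 31/480 = 6.5%, and (6 + 6 + 19)/480 = 31/480 = 6.5%. The tables are identical.
4. By coded arm, first against third, with Wald interval d ± 1.96 × √[p₁(1 − p₁)/160 + p₃(1 − p₃)/160] and Fisher's exact test:
   - 10/160 against 11/160: d = 0.6 points, 95% CI −4.8 to 6.1, p = 1.00.
   - 6/160 against 19/160: d = 8.1 points, 95% CI 2.3 to 13.9, p = 0.011.
5. With assumed risks of 5%, 5% and 10%, the pooled figure is (8 + 8 + 16)/480 = 6.7%, close to the 6.5% above.

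A table labelled only 1, 2 and 3 separates these cases without revealing which treatment is which.

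**Point (b): routes and volume**

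| Event | DSMB | IRB (as stated in 8.1 and 8.2) |
|---|---|---|
| Fatal | Within 72 hours | Within 72 hours |
| Non-fatal SAE, including life-threatening | Monthly report | No route stated |

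How many infants are dosed in one monthly cycle depends on recruitment speed, which the documents do not give. Protocol section 3 gives about 5000 births a year. If 10% to 30% were enrolled (assumed), then 5000 × 0.10/12 = 42 to 5000 × 0.30/12 = 125 dyads a month would be randomised. One third in the azithromycin arm is 14 to 42 infants. This treats monthly dosing as equal to monthly enrolment and ignores dropout.

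**The case against.** **On (a).** A reader might infer that the harm rule cannot be applied at all, or that one stopping rule lacks its input however the text is read. The documents do not support this. The interim subsection opens by promising coded differences in primary, secondary and SAE outcomes, which is what both the harm and the benefit rule need. The SAP repeats the promise without the pooling sentence. The DSMB can also request analyses and open the codes. A benign reading is available too: coded differences are supplied, and site-specific and overall summaries are shown pooled in addition. All of this stands. What remains is that the pooling sentence follows directly on a list containing SAEs and the growth outcomes and states no such limit. The SAP's silence does not cancel a Protocol instruction.

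**On (b).** Slow reporting between interims does not prevent arm differences from being computed at an interim, so (b) is not a cause of (a). Nor do the documents show that nobody able to pause dosing would have seen the event: study physicians and the senior team assess each suspected event, and the documents do not say that only the DSMB can pause. Protocol 8.1 says that supplement reporting follows FDA guidelines, and the IRB or a DSMB charter may set its own timelines; none of these can be seen here. That is fair, but 8.2 makes no such reference for azithromycin, and the only times stated in either section are monthly and, for deaths, 72 hours. The documents also do not say whether the monthly reports are split by arm, so no claim is made on that.

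**Conclusion.** Both points hold, separately and in limited form.

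(a) Protocol section 10 is internally inconsistent on whether the DSMB receives interim SAEs and outcomes pooled or by coded arm. It must be reconciled with its own stopping guidelines and with SAP section 15. The weight of the text favours coded arms, so this is a contradiction to remove and not a safety rule that fails. It deserves attention because a statistician who followed the pooling sentence literally would hand over tables that cannot feed the harm rule. The 6.5% and 6.7% pooled figures show how that could happen; they rest on assumed SAE counts and do not measure anything in this trial.

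(b) Protocol 8.1 and 8.2 state no route faster than monthly to the DSMB, and none to the IRB, for non-fatal life-threatening events. The figure of 14 to 42 infants dosed per cycle rests on the assumed 10% to 30% enrolment fraction and shows scale only.

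**What to change.** **(a)** In Protocol section 10, delete the pooling sentence, or limit it to an open report or to supplementary site and overall summaries. State that the DSMB's closed interim report gives SAEs, deaths, and primary and secondary outcomes by coded arm (1, 2, 3), prepared by the independent statistician. Use the same wording in SAP section 15. The cost is a few lines of text, since the codes, the sealed file and the independent statistician are already in place.

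**(b)** In Protocol 8.1 and 8.2, extend the existing 72-hour DSMB and IRB route to non-fatal life-threatening SAEs, at least those judged related, and name the relatedness categories that count. The adverse-event form and the relatedness scale already exist. The cost is a few more expedited reports. Any decision on treatment stays with the DSMB.
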